The phase begins after the last administration of the IMP. It lasts 1 week after the last administration of the IMP.

- Visit 17: 1 week after the last administration of the IMP, the end of study.

At this phase, a set of laboratory tests is assessed and vital signs are measured. Registration of AEs/ARs is also performed.

The results of the study are entered into the eCRF, according to the Schedule of Study Procedures (see Table 4.2.1).

The procedures and phases are listed in Tables 4.2.1–4.2.3

Tabular schedule of study procedures

Table 4.2.1. Schedule of study procedures.

Visits	Visit 1	Visit 2	Visit 3	Cycle 1 Weeks 1–4			Cycle 2 Weeks 5–8			Cycle 3 Weeks 9–12			Cycle 4 Weeks 13–16			Cycle 5 Weeks 17–20			Cycle 6 Weeks 21–24		
Study phase	Screening period ∞						Treatment period														
Procedures / Time point	Day 0	Day 21–28	Day 42–56	Week 1 (C1W1)	Weeks 2–4 (C1W2-C1W4)	Week 5 (C2W5)	Weeks 6–8 (C2W6-C2W8)	Week 9 (C3W9)	Weeks 10–12 (C3W10-C3W12)	Week 13 (C4W13)	Weeks 14–16 (C4W14-C4W16)	Week 17 (C5W17)	Weeks 18–20 (C5W18-C5W20)	Week 21 (C6W21)	Weeks 22–24 (C6W22-C6W24)	Week 25 (C7W25)	Weeks 26–28 (C7W26-C7W28)				
Informed Consent signing	●																				
Collection of demographics	●																				
Collection of anthropometrics ¹	●	X	X	X	X	X	X	X	X	X	X	X	X	X	X	X	X	X	X	X	
Collection of medical history ²	●																				
Data on antibiotic therapy and concomitant therapy	●	●	●	●	●	●	●	#	●	#	●	#	●	#	●	#	●	#	●	#	
Presence of infections	●	●	●	●	●	●	#	●	#	●	#	●	#	●	#	●	#	●	#	●	
Physical examination ³	●	●	●	●			●		●	X		X			●		X				
Vital signs ⁴	●	●	●	●			●		●		●		●		●		●		●		
Chest X-ray/CT/MRI ⁵	X																				
12-lead ECG;	●																				
Complete blood count ⁶	●			●		●								●							
Serum chemistry ⁷	●			●		●								●							
Direct Coombs' test (antiglobulin test) ⁸	●	X	X	●		●		X		X		X		X		X		X			

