¹ Height, body weight, BMI. x – Starting from Visit 2, only body weight is measured² Confirmation of underlying disease, information on administration of prior therapy ([type of therapy, dose/schedule, duration, time interval since the last administration], transfusion history, allergy history, infectious history, comorbidities, information on therapy for comorbidities, presence/absence of harmful habits).³ auscultation and percussion of the heart and lungs; palpation and percussion of abdominal organs; examination of the skin and mucous membranes; x – at visits where not mandatory, performed in a suspected infection⁴ BP, HR, RR, Body t°;⁵ The screening chest X-ray/CT/MRI is only performed if there has been no such assessment during the last 6 months prior to enrolment.⁶ Haemoglobin, haematocrit, red blood cells, white blood cells and white blood cell differential, and platelets;⁷ ALT, AST, total bilirubin, creatinine, urea, glucose;⁸ x – if haemolysis is detected based on laboratory results, the Coombs' test may be performed at any visit at the Responsible Investigator's discretion;

Haptoglobin level ⁹	●	X	X	●		●		X		X		X		X		X
Threshold level of total serum IgG (pre-administration) ¹⁰	●	●	●	●		●		●		●		●		●		●
Total serum IgG level (PK assessment) ¹¹			●											●		
Urinalysis ¹²	●			●		●					●					
HIV test (express test), RW, HBs-Ag, anti-HCV	●															
Pregnancy test (for women of childbearing potential) ¹³	●	X	X	X			X		X		X		X		X	
Coagulation panel (INR, Prothrombin percentage by Quick, Prothrombin time, aPTT, fibrinogen)	●	X	X	X		●		X		X		●		X		X
Glycated haemoglobin	●															
Assessment of inclusion and non-inclusion criteria during the screening	●	●	●													
Assessment of exclusion criteria	●	●	●	●		●		●		●		●		●		●
Assigning the date of the next visit	●	●	●	●		●		●		●		●		●		●
Issuance of IMP for interim administrations						●		●		●		●		●		●
Administration of the study drug			●	●	●	#	●	#	●	#	●	#	●	#	●	#
Checking the used IMP vials						●		●		●		●		●		●
Registration of AEs/ARs	●	●	●	●	●	●	#	●	#	●	#	●	#	●	#	●
Filling in the patient's questionnaire				●		●						●				
Checking the completion of patient's diary							●		●		●		●		●	
Telephone contact with the patient						●		●		●		●		●		●

⁹ x – if haemolysis is detected based on laboratory results, testing for haptoglobin levels may be performed at any visit at the Responsible Investigator's discretion;

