8.2 AE detection and documentation

The identification and registration of AEs begins from the time of signing the informed consent and continues until the end of the given patient's participation in the study.

AE identification and registration starts from the moment of drug administration and continues until the end of the patient's participation in the study.

The AEs that occur between the screening and drug administration and that are not SAEs must be recorded as medical history.

All AEs occurring from the moment of drug administration, which are reported by the patient or identified during the follow-up, physical examination and other diagnostic procedures, shall be registered in the AE Report Form, which is a structural constituent of the eCRF.

Laboratory findings will be evaluated during screening and throughout the study.

Information on any AEs observed during the study period, starting with the first administration of the investigational product and up to the end of investigational product use is documented in medical records/outpatient card of the patient and under the AE section in the eCRF. All AEs must be documented, regardless of their severity or causality with the investigational medicinal product.

The following events **must** be classified as AEs:

- exacerbations/flare of pre-existing conditions;
- increase in incidence or severity (intensity) of diseases or previously observed episodic events;
- any disease(s) detected or diagnosed after the onset of treatment with the investigational medicinal product, even if it was possible for the disease(s) to be present before the start of patient's participation in the study;
- any prolonged and/or persistent illnesses or symptoms present at baseline, the severity of which increased after the patient joined the study;
- new signs or any increase in severity of signs and symptoms of diabetes that required immediate treatment, hospitalisation, surgery and/or any other intervention;
- any clinically significant abnormalities of laboratory results or findings of other tests occurring after the onset of treatment with the investigational product, or any such baseline abnormalities, the severity of which increased in a setting of treatment with the investigational medicinal product.

The following events **shall NOT** be classified as AEs:

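### Section 8.2 gives conflicting adverse event recording windows, so sites can differ on whether screening events and the week after the last infusion are recorded

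*Protocol*

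**What the plan says.** Section 8.2 states the recording period three times.

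- The first sentence reads "The identification and registration of AEs begins from the time of signing the informed consent", and it runs to the end of the patient's participation.
- The next paragraph reads "AE identification and registration starts from the moment of drug administration", and it too runs to the end of participation.
- Further on, the events to be documented in the medical records and in the AE section of the eCRF are those observed "starting with the first administration of the investigational product and up to the end of investigational product use".

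Other text in 8.2 also bears on the start. One sentence reads "The AEs that occur between the screening and drug administration and that are not SAEs must be recorded as medical history". The AE Report Form is said to take "All AEs occurring from the moment of drug administration". Items 1 and 4 of the list of events that are not AEs exclude two kinds of finding: conditions detected before treatment that do not worsen, and clinically significant laboratory abnormalities detected before the first dose.

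Section 4.2 says otherwise at both ends. The row "Registration of AEs/ARs" in Table 4.2.1 is marked as mandatory at screening Visits 1, 2 and 3 and at Visit 17. The follow-up text says of Visit 17 that "Registration of AEs/ARs is also performed".

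**The concern.** The recording window is an instruction to sites. An analysis plan can filter recorded events by onset date, but it cannot recover events that a site was told not to record.

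The overall frequency of AEs is a safety endpoint in Section 4.1, listed apart from treatment-emergent events. The AE analysis in 9.5 is a frequency and percentage with no onset-date rule. The safety population in 9.1 restricts which subjects count (at least one dose), not which event dates count. During screening, Cohorts A and B continue their previous SCIG or IVIG, and adults in Cohort B have a BIOVEN infusion with serial sampling from Visit 3. Depending on the sentence followed, non-serious events from that time are AEs or medical history.

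At the other end, the last infusion is given at home and Visit 17 follows a week later. A site working to the third sentence would stop recording before that visit. Section 8.4 would then bring back only events with sufficient evidence of a relationship to the product.

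This is a single-arm study, so no control group would reveal uneven recording.

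**Working it through.** There is no stated figure to reproduce. The check sets the passages side by side and adds up the window lengths.

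**Start of the window**

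- Consent: first sentence of 8.2; Table 4.2.1 at Visits 1 to 3.
- First dose: second and third window sentences, AE Report Form sentence, medical-history sentence (non-serious events only), and items 1 and 4 of the not-an-AE list.
- The second window sentence says drug administration without naming the investigational product, although BIOVEN is given during screening.

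**End of the window**

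- End of participation: first and second window sentences; Table 4.2.1 and the 4.2 follow-up text at Visit 17.
- End of product use: third window sentence.

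There are therefore two starts and two ends. The medical-history sentence addresses only the start, and it exempts serious events.

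**Lengths**

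Inputs, from Sections 4.2 and 4.5: weekly doses 1 to 52; Visit 17 one week after the last dose; Visit 2 on Day 21–28; Visit 3 on Day 42–56; BIOVEN sampling over 21–28 days from Visit 3; screening up to 2 months.

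- First to last dose: 52 − 1 = 51 weeks.
- First dose to Visit 17: 51 + 1 = 52 weeks.
- Consent to Visit 17: 52 weeks plus the screening time.

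| Patients | Screening (weeks) | Consent to Visit 17 (weeks) | Screening / 52 |
|---|---|---|---|
| Cohort A and paediatric Cohort B, ending at Visit 2 | 3–4 | 55–56 | 6–8% |
| Screening to Visit 3 | 6–8 | 58–60 | 12–15% |
| Adult Cohort B, if BIOVEN sampling finishes before the first dose | 9–12 | 61–64 | 17–23% |
| Cohort C, Visit 1 only, taken as about 0 weeks | about 0 | about 52 | about 0% |

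The endpoints are 3/52 = 5.8%, 8/52 = 15.4% and 12/52 = 23.1%. The third row rests on an assumption: Visit 3 on Day 42–56 plus 21–28 days of sampling gives 63–84 days, which exceeds the screening period of up to 2 months in Section 4.5. The same section's total of about 62 weeks per patient leaves 62 − 52 − 1 = 9 weeks for screening.

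The third window omits 52 − 51 = 1 week, which is the follow-up period.

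**The case against.** The best defence is that 8.2 can nearly be read as one coherent rule. The medical-history sentence, the AE Report Form sentence, the eCRF sentence and items 1 and 4 of the not-an-AE list all point to a first-dose start, which leaves the opening sentence as the outlier. Registration at Visits 1 to 3 can then mean asking about events, registering the serious ones and moving the rest to medical history. At the other end, two of the three window sentences, Table 4.2.1 and the follow-up text all reach Visit 17, and 8.2 requires AEs to be monitored until adequately resolved. AE onset dates are recorded, so events before the first dose can be separated in analysis.

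Much of this stands, and it limits the consequence. It does not remove the contradiction. The opening sentence is not confined to serious events, the schedule marks registration without that limit, and the third sentence remains incompatible with Visit 17.

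A reader might infer more than the documents support:

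- *That sites will count different events.* The text shows only that they can. A site that applies the medical-history sentence keeps non-serious events before dosing out of the AE record.
- *That reactions to the previous product distort the safety profile of the new one.* Section 4.1 defines adverse reactions as reactions to the investigational product and lists treatment-emergent events separately. The exposure is mainly in overall AE frequency.
- *That up to 23% of time is at issue throughout Cohorts A and B.* The 12-week figure can arise only in adult Cohort B and needs the sampling assumption above.

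**Conclusion.** The point holds as an internal contradiction in 8.2, and between 8.2 and the schedule, over both the start and the end of AE recording. Its effect falls mainly on the overall frequency of AEs, through non-serious screening events, and on the completeness of the last week. Treatment-emergent events and adverse reactions to the product are less affected, provided that treatment-emergent is counted from the first infusion.

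For Cohorts A and B, the disputed screening time is about 3–4 weeks (to Visit 2) or 6–8 weeks (to Visit 3), which is about 6–15% of 52 weeks. It reaches 12 weeks (23%) only for adults in Cohort B, and only if the first dose waits for the end of BIOVEN sampling. These are shares of time. The protocol gives no event rates, so they cannot be converted into shares of AE counts. The disputed time at the end is one week.

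The correction should be made, because it is inexpensive and protects the completeness and attribution of single-arm safety data.

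**What to change.** State one start and one end for AE recording in 8.2, consistent with Table 4.2.1 and ending at Visit 17; consent to Visit 17 is the obvious example. Then align all the conflicting text with it:

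- the second and third window sentences;
- the medical-history sentence;
- the AE Report Form sentence;
- items 1 and 4 of the not-an-AE list.

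Removing only the second and third window sentences would leave the other texts in conflict.

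Add that AE frequencies for the investigational product count events with onset or worsening at or after its first infusion, and that earlier events are listed separately.

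The cost is wording, plus a few more non-serious screening entries in the eCRF. No visit or procedure is added, since the schedule already registers AEs at these visits.

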The recommended infusion rate must be followed strictly. During the initial administration, the patients shall remain under supervision for the entire duration of the infusion period to detect hypersensitivity to the active ingredient or to any of the excipients. Monitoring for any adverse symptoms shall be in place. It is forbidden to administer the IMP BP-SCIG 20% in pronounced thrombocytopenia or other disorders of haemostasis.

Potential complications described in this Protocol (see Section 2, item 3) can usually be avoided in adherence to:

- slow start of administration, from the infusion rate of 10 mL/kg/line;
- careful monitoring of patients' well-being in relation to any symptoms throughout the infusion period. In particular, patients who have not previously received human normal immunoglobulin, patients who have switched from an alternative immunoglobulin product, or if a long period of time has passed since the previous administration shall be monitored by health care workers during the first infusion and throughout the first hour afterwards to identify any potential adverse manifestations.

In all other cases, the patient's well-being must be monitored for at least 20 minutes after the administration.

In case of an adverse reaction, either the infusion rate must be reduced, or administration must be stopped. If an AE develops, the necessary treatment will depend on the nature and the severity of the AE.

The route of administration and dosing shall not exceed the maximum single and course doses that can be used in patient treatment, within the limits specified in "*Guideline on core SmPC for human normal immunoglobulin for subcutaneous and intramuscular administration*" EMA/CHMP/BPWP/143744/2011 rev.1 26 February 2015, and "*Guideline on the clinical investigation of human normal immunoglobulin for subcutaneous and/or intramuscular administration (SCIg/IMIg)*" EMA/CHMP/BPWP/410415/2011 rev.1 23 July 2015.

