1. any diseases or abnormalities, which were detected or diagnosed before the start of treatment with the investigational medicinal product, the severity of which does not increase;
2. situations where no adverse medical occurrence is present (e.g. hospitalisation for an elective surgery);

3. overdose of any investigational medicinal product(s) or concomitant medicinal product(s) without any adverse signs or symptoms;
4. any clinically significant laboratory abnormality detected before first dose of the investigational product;
5. signs and symptoms observed during the study that are associated with lack of adequate response to treatment.
6. Death occurring under force majeure circumstances (as defined by Ukrainian law)

The emergence of any adverse events (AEs) will be tracked during the study. Table 8.2.1 presents the treatment tolerability scale.

Table 8.2.1. Treatment tolerability scale

Category	Category description
Good	An objective overview over time shows no abnormal changes or clinically significant deviations, data of the laboratory examination do not change significantly and remain within the normal; the patient does not report any manifestations of adverse reactions
Satisfactory	An objective overview over time shows minor transitory changes that require no modifications in the treatment schedule or additional medical interventions and/or laboratory examination data are insignificantly outside normal limits and/or insignificant adverse reactions are observed that do not cause serious problems for the patient and do not require discontinuation of the product
Unsatisfactory	An objective review over time shows abnormal changes that require discontinuation of the drug and additional medical interventions and/or laboratory findings are subject to clinically significant adverse changes, entailing the need for additional examinations and interpretation of data and/or there is an adverse side reaction that has a significant negative effect on the patient's condition and requires the discontinuation of the product and additional medical interventions

Signs and symptoms underlain by general disease shall, if possible, be indicated as a single complex event. If the diagnosis is known, it must be registered as the name of the AE. If the diagnosis is not known, each complaint and symptom must be registered as a separate AE.

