9. STATISTICS

9.1. Contents of statistical analysis

Subjects who withdrew during the screening phase are not counted in the efficacy and safety analysis since they have not received any administration of the investigational medicinal product (IMP).

Subjects who have not received a full IMP course are included in the safety analysis, but are not included in the efficacy analysis.

Subjects who discontinued from the study after completing IMP administration during the follow-up period are included in the efficacy and safety analysis. The data of such subjects are evaluated by parameters that may be analysed at a certain time point. The dropped data are not analysed.

Subjects who received at least one dose of the IMP but withdrew from the study prematurely are included by the Investigator in the tolerability analysis of the investigational product.

Statistical analysis:

Populations for statistical analysis:

ITT (Intention-to-treat population) includes all study subjects who received the investigational product at least once. The data obtained from this sample will be used for the safety analysis.

PP (Per Protocol) includes all patients who complied with the protocol requirements. This population includes all patients who received full protocol therapy, who underwent all scheduled visits, and did not have significant protocol deviations. The data obtained from this sample will be used for analysis by efficacy criteria.

The main efficacy analysis is performed on the PP population, and the additional, confirmatory analysis is performed on the ITT population (all subjects who received ≥ 1 dose and who meet the inclusion criteria, and for whom efficacy can be established).

Plan of statistical analysis of CS results

Statistical analysis is performed by a qualified biostatistician, a third party contracted by the Sponsor. Statistical analysis includes the following:

- description of patients enrolled in the study;
- the number of drop-out subjects;
- the number of adverse events;
- efficacy analysis in the group;
- tolerability assessment in the group;
- safety assessment in the group;
- analysis of pharmacokinetic data;
- statistical inferences.

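### The tolerability scale in Table 8.2.1 is neither exhaustive nor mutually exclusive: significant reactions that are treated while dosing continues, and reactions that merely end treatment, meet no reaction criterion

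*Protocol*

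**What the plan says.** Tolerability is part of the fourth primary objective (Section 3). Section 9.1 lists "tolerability assessment in the group" as an analysis item separate from the safety assessment. The only scale for it is Table 8.2.1 in Section 8.2, which has three categories.

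- **Good** requires no abnormal changes on examination, laboratory data within normal limits, and no reported reaction.
- **Satisfactory** has three criteria joined by and/or: minor transitory examination changes needing neither a schedule modification nor extra intervention; laboratory data slightly outside normal limits; or "insignificant adverse reactions are observed that do not cause serious problems for the patient and do not require discontinuation of the product".
- **Unsatisfactory** also has three criteria joined by and/or. For examination findings: "An objective review over time shows abnormal changes that require discontinuation of the drug and additional medical interventions". For laboratory data: "laboratory findings are subject to clinically significant adverse changes, entailing the need for additional examinations and interpretation of data". For reactions: an adverse reaction with a significant negative effect that also "requires the discontinuation of the product and additional medical interventions".

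Elsewhere the protocol treats stopping and treating as different things. Section 6.1 says that in case of an adverse reaction "either the infusion rate must be reduced, or administration must be stopped". The list of actions to be recorded for each adverse event in Section 8.2 has discontinuation, dose reduction and pharmacological therapy as separate entries.

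**The concern.** A rating scale must give each patient one category. Here the reaction criterion of Unsatisfactory sets three conditions that must all hold, and Satisfactory starts only at insignificant reactions. The space between them is not assigned. It contains outcomes that the protocol foresees, such as a reaction handled by lowering the infusion rate while dosing goes on, or one treated with medication while dosing goes on.

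The study is open-label, single-arm and multicentre. An investigator who meets an uncovered case has to improvise, and sites may do so differently. The share of patients in each category would then depend partly on local reading of the table and could not be compared between sites or reproduced from the recorded data.

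**Working it through.** The protocol states no figure for this point, so the check takes the table literally and enumerates what it covers.

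**Inputs.** The category conditions come from Table 8.2.1. The separate handling of rate reduction, stopping and treatment comes from Section 6.1 and from the list of recorded actions in Section 8.2.

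**Step 1: reaction criteria.** With no reaction there is one case. An insignificant or a significant reaction can each occur with or without discontinuation and with or without additional intervention. The count is 1 + 2 × 2 × 2 = 9.

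| Reaction | Discontinued | Intervention | Reaction criterion met |
|---|---|---|---|
| None | – | – | Good |
| Insignificant | No | No | Satisfactory |
| Insignificant | No | Yes | Satisfactory |
| Insignificant | Yes | No | none |
| Insignificant | Yes | Yes | none |
| Significant | No | No | none |
| Significant | No | Yes | none |
| Significant | Yes | No | none |
| Significant | Yes | Yes | Unsatisfactory |

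Four combinations are covered and 9 − 4 = 5 are not. Of the four with a significant reaction, three are uncovered. A reaction handled by rate reduction alone sits in a row without discontinuation, so a significant one is uncovered.

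**Step 2: objective-change criteria.** Discontinuation (yes/no) by intervention (yes/no) gives 4 combinations. Both together is Unsatisfactory. Neither is Satisfactory, provided the change is minor and transitory and the schedule is not modified. The two combinations with only one of them meet no objective-change criterion.

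**Step 3: effect of and/or.** The table rates a patient, and one criterion is enough for Satisfactory or Unsatisfactory. Three patients show the result:

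- A significant reaction, treated, dosing continued, and one laboratory value slightly outside normal. No reaction criterion is met. The laboratory criterion of Satisfactory is met, so the literal rating is Satisfactory.
- No reaction, and a clinically significant laboratory change that needs further examinations but neither treatment nor discontinuation. The literal rating is Unsatisfactory.
- A significant reaction with discontinuation and intervention, and one laboratory value slightly outside normal. Both Unsatisfactory and Satisfactory are met, and the table has no rule on which prevails.

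So the categories leave gaps, overlap, and can rank a treated significant reaction better than a laboratory finding that only needs follow-up tests.

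**Step 4: the same enumeration after the change proposed below.** All four significant rows and both insignificant rows with discontinuation become Unsatisfactory (6). The two insignificant rows without discontinuation stay Satisfactory (2). No reaction stays Good (1). The total is 6 + 2 + 1 = 9, with none uncovered.

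**The case against.** The strongest reply is that little depends on the scale. The safety and tolerability endpoints in Section 4.1 are frequencies of events, reactions and clinically significant deviations. Section 9.5 analyses laboratory values, vital signs and adverse events. Neither of these sections names the scale, nor do the visit schedule and the eCRF list. Severity, causality, seriousness and measures taken are recorded for each adverse event. This stands: individual safety data are not lost and no hypothesis test is affected. It does not remove the defect, because Section 9.1 lists a tolerability assessment of its own and the protocol offers no other scale for it.

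A second reply is that an uncovered reaction does not mean an unrated patient. This also stands. The count of 5 in 9 refers to the reaction criteria, and a patient may still be rated through laboratory or examination findings. But that route is what allows the rating to ignore a significant reaction.

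A reader might go further and infer that the Unsatisfactory rating can hardly occur. The documents do not support that. The laboratory criterion suffices alone and requires neither discontinuation nor treatment. The rating is hard to reach only through the reaction and objective-change criteria.

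A reader might also infer a known bias in favour of the product, or a number of unclassifiable patients among the 56. Neither follows. The protocol does not say how uncovered cases are to be handled, and it gives no rate of significant reactions managed without stopping.

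**Conclusion.** The concern holds as a defect of classification. Five of nine reaction combinations, including three of the four with a significant reaction, meet no reaction criterion. The objective-change criteria fail for two of four combinations, and the and/or joins create overlaps without an order of precedence. The conclusion rests on a literal reading of Table 8.2.1 and on no assumed event rate.

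The consequence is limited to the tolerability rating. The primary efficacy test, the pharmacokinetic analyses and the adverse event tables are untouched. The change is worth making because this is the only scale given for a listed analysis and the correction is cheap.

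**What to change.** Reword Table 8.2.1 as an outcome classification only, with no change to when a reaction is treated or the product is stopped.

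- **Unsatisfactory, reaction criterion:** significant negative effect on the patient's condition, or led to discontinuation.
- **Unsatisfactory, objective-change criterion:** led to discontinuation, or needed additional medical intervention.
- **Unsatisfactory, laboratory criterion:** keep as it is. Do not add a condition that the finding be related to the product.
- **Satisfactory:** any other reaction or change.
- **Good:** none.
- **Precedence:** the worst applicable criterion decides the category.

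In Section 9.1, state that the tolerability assessment in the group uses this scale in all subjects who received at least one dose. That section already places subjects who received a dose and withdrew early in the tolerability analysis, so this only links the scale to a population largely defined there.

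The cost is one reworded table and one added sentence. The downside is that the share rated Unsatisfactory may be somewhat higher.
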